8.2 Sample Size Determination

Randomly assigning 80 participants to each of the three study arms will give approximately 80% power to conclude that at least one of the alternative follow-up strategies is non-inferior to conventional follow-up, using a 15% non-inferiority margin. This controls for multiple testing at the 5% level and assumes an analysis based on a logistic mixed model. We will additionally test the non-inferiority of “Patient-initiated care” to “Remote monitoring” using the same 15% margin. This test will be done only if “Patient-initiated care” is shown to be non-inferior to conventional care (a hierarchical test), and thus will not inflate the 5% false positive rate.

8.3 Analysis Sets

Population	Description
Enrolled	The Enrolled set will include all patients who have provided informed consent and have been included into the study data base.
Intention to Treat Set	The Intention to Treat (ITT) Set will include all patients randomly assigned to a study arm irrespective of post randomization occurrences.
Full Analysis Set	The Full Analysis Set (FAS) will be defined as all patients randomly assigned to a study arm and that have started the allocated intervention defined as having completed at least one assessment of the primary endpoint at 6, 12 or 18 months. The FAS will form the primary analysis set of the study and will be used for primary non-inferiority analyses.
Completer Analysis Set	The Completer Analysis Set will include all randomized patients having started the allocated intervention and not withdrawn during the study.
Per Protocol Analysis Set	The Per Protocol Analysis Set (PPS) will include all randomized patients meeting the study entry criteria who followed the study protocol with no major protocol deviations.

8.4 Statistical Analyses

The statistical analysis plan (SAP) will be finalized prior to un-blinding and it will include a more technical and detailed description of the statistical analyses described in this section. This section is a summary of the planned statistical analyses of the most important endpoints including primary and key secondary endpoints.

8.4.1 General Considerations

- Efficacy (both primary and secondary endpoints) and safety analyses will include data from all randomised patients who started the allocated intervention by attending at least one completed questionnaire and blood test result after randomisation (FAS), and robustness analyses will be performed in the PPS.
- Demographics, baseline characteristics, efficacy and safety variables will be summarised using descriptive statistics.
- All efficacy analyses will be presented with the results from the hypothesis testing (by p-value) in addition to estimates and 95% confidence limits of the treatment effect. For the primary variables specifically, this will be the estimated mean probability with corresponding 95% confidence limits.

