6.2 Participant Discontinuation/Withdrawal from the Study

Patients have the right to withdraw from the study at any time for any reason. In the case that a patient decides to prematurely withdraw from the study, he or she should be asked if they can still be contacted for further information, so that a final evaluation can be made with an explanation of why the patient is withdrawing from the study, including assessment of possible adverse events. Although a subject is not obliged to give his or her reason(s) for withdrawing prematurely from a trial, the investigator should make a reasonable effort to ascertain the reason(s), while fully respecting the subject's rights. If possible, at the last visit of the patient all assessments of the "Early discontinuation of study visit" will be done.

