7.3.1 Physical Examinations

- General clinical examination (baseline visit)

7.3.2 **Vital signs**

- Pulse and blood pressure (baseline visit)
- Height and weight (baseline visit)

7.3.3 **Clinical Safety Laboratory Assessments** (every 3rd month and all visits)

- Haemoglobin, red blood cells, white blood cells with differential count and platelet count
- Glomerular filtration rate (GFR) and creatinin
- Alanine transaminase (ALT)

7.3.4 **Adverse Events (AEs), Serious Adverse Events (SAEs), and Other Safety Reporting**

The definitions of adverse events (AEs) and serious adverse events (SAEs) as well as the method of recording, evaluating, and assessing causality of AEs and SAEs and the procedures for completing and transmitting SAE reports are provided in Appendix 3.

7.3.5 **Time Period and Frequency for Collecting AE and SAE Information**

All AEs and SAEs will be collected from the start of intervention until the final follow-up visit at the time points specified in Schedule of Activities. Medical occurrences that begin before the start of study intervention, but after obtaining informed consent, will be recorded as Medical History/Current Medical Conditions, not as AEs. All SAEs, including updates, will be recorded and reported to the sponsor or designee immediately, as indicated in Appendix 3. Investigators are not obligated to actively seek information on AEs or SAEs after conclusion of the study participation.

7.3.6 **Method of Detecting AEs and SAEs**

Care will be taken not to introduce bias when detecting AEs and/or SAEs. Open-ended and non-leading verbal questioning of the participant is the preferred method to inquire about AE occurrences.

7.3.7 **Follow-up of AEs and SAEs**

After the initial AE/SAE report, the investigator is required to proactively follow each participant at subsequent visits/contacts. All SAEs will be followed until resolution, stabilization, the event is otherwise explained, or the participant is lost to follow-up.

7.3.8 **Regulatory Reporting Requirements for SAEs**

Prompt notification by the investigator to the sponsor of an SAE is essential so that legal obligations and ethical responsibilities are met. The sponsor has a legal responsibility to notify both the local regulatory authority and other regulatory agencies about the safety of a study intervention under clinical

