8.4.4 Safety Analysis

Rates and type of adverse events and serious adverse events in all three study arms will be reported.

9 Supporting Documentation and Operational Considerations

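### Section 8.4.1 admits patients to the safety analyses only if they supply a questionnaire and a blood result after randomisation, so early deaths and leavers with an event can drop out of the between-arm comparison

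*Protocol*

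**What the plan says.** Section 8.4.1 sets one population for efficacy and safety together: "safety analyses will include data from all randomised patients who started the allocated intervention by attending at least one completed questionnaire and blood test", both obtained after randomisation, with the label FAS. It adds that "robustness analyses will be performed in the PPS".

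Section 8.4.4, on safety, says "Rates and type of adverse events and serious adverse events in all three study arms will be reported". It names no analysis set.

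Section 8.3 defines an ITT Set that "will include all patients randomly assigned to a study arm irrespective of post randomization occurrences", but neither 8.4.1 nor any other stated analysis uses it. There is no separate safety set. The same section bases FAS membership on "having completed at least one assessment of the primary endpoint at 6, 12 or 18 months", which is not the condition in 8.4.1.

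On data collection, section 7.3.5 says "All AEs and SAEs will be collected from the start of intervention until the final follow-up visit", and that "All SAEs, including updates, will be recorded and reported to the sponsor or designee immediately". Collection does not depend on a questionnaire or a blood sample.

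**The concern.** Entry to the safety analyses depends on two items that a patient can supply only after randomisation. Events are collected from the start of the intervention, so there is a period in which a patient can have a recorded event and not yet belong to the analysis set. If the event leads to death or departure in that period, the event and the patient both leave the comparison.

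Comparing the safety of the two new strategies with usual care is a secondary objective (section 2.3.4). The risk table in section 2.3.1 names failure to self-report or to register blood results as a way in which adverse events could be missed in the new arms. Section 8.4.1 makes those same two items the entry condition for the safety analyses.

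This is not a detail left to the SAP. The protocol states the population itself, and section 8.4 describes the SAP as a more technical account of the analyses set out there.

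**Working it through.** **Step 1: which set applies to AEs and SAEs.** Section 8.4.4 is silent, so the general rule in 8.4.1 governs. The fallback, the PPS, is also conditional on conduct after randomisation and does not repair the gap. The ITT Set would, but no analysis is assigned to it.

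**Step 2: when a patient can first qualify under 8.4.1.**
- Questionnaires (section 7.2.1): monthly in remote monitoring, every third month in patient-initiated care, every sixth month in usual care.
- Blood results: uploaded every sixth month in the two new arms (7.2.3). In usual care the first pre-scheduled visit is at month 6 (5.1.2).
- Earlier routes: an unscheduled visit includes the regular assessments where feasible (7.1.5), and Appendix 2 (9.2) places safety laboratory tests at any hospital visit. The withdrawal visit covers the regular assessments (7.1.7), but section 6.2 makes it conditional: "If possible, at the last visit of the patient all assessments of the" early-discontinuation visit are done.

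The affected patient is one who, in any arm, has an event and never supplies both items. Because the scheduled opportunities differ by arm, exclusion could too.

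**Step 3: the two FAS definitions.** If the FAS label in 8.4.1 is read as in 8.3, a patient who leaves before month 6 is out of the safety analyses even after a complete withdrawal visit. The primary mixed-model estimate is the same under either wording: a patient who qualifies only under 8.4.1 has no ASDAS at 6, 12 or 18 months and contributes no outcome. What changes is the FAS count and who is in the safety and secondary analyses. An example is a patient with half-yearly questionnaires whose only blood result is the standard panel of 7.2.3, which lists neither CRP nor ESR.

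**Step 4: size.** The protocol gives 80 per arm (8.2) and no event rate, so there is no stated figure to reproduce. Let x be the patients with an SAE in an arm and k those of them who never supply both items (both assumed). The risk moves from x/80 to (x − k)/(80 − k).

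| x | k | All randomised | Section 8.4.1 set | Change (points) |
|---|---|---|---|---|
| 1 | 1 | 1/80 = 1.25% | 0/79 = 0% | −1.25 |
| 2 | 2 | 2/80 = 2.50% | 0/78 = 0% | −2.50 |
| 4 | 1 | 4/80 = 5.00% | 3/79 = 3.80% | −1.20 |
| 4 | 2 | 4/80 = 5.00% | 2/78 = 2.56% | −2.44 |
| 8 | 1 | 8/80 = 10.00% | 7/79 = 8.86% | −1.14 |
| 8 | 2 | 8/80 = 10.00% | 6/78 = 7.69% | −2.31 |

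Exact (Clopper-Pearson) 95% intervals: 1/80, 0.03 to 6.8%; 0/79, 0 to 4.6%; 2/80, 0.3 to 8.7%; 0/78, 0 to 4.6%.

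Losing patients without an SAE moves the risk the other way. With x = 8 and four such leavers, 8/80 = 10.00% becomes 8/76 = 10.53% (+0.53 points).

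**The case against.** The best counter-argument is that the affected group is small. A patient in any arm who suspects an adverse event is to contact the hospital and be seen within two weeks (7.1.5), and safety bloods are taken at any hospital visit (9.2). Reporting an event therefore tends to generate the blood result, and often the questionnaire. The three-monthly blood tests may also count under the loose wording of 8.4.1. This narrows the group, mainly to sudden deaths and to events never followed by a contact. It does not empty it: full assessments at unscheduled and withdrawal visits are both conditional on feasibility, and neither helps after an early death.

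Second, AE review takes place at months 6, 12 and 18 and at extra or discontinuation visits (section 1.3). A patient with none of these contacts would count as event-free in an all-randomised denominator, which dilutes the AE rate a little. That is true, and it is a cost of the fix, mainly for non-serious events. It is smaller than the harm of discarding events already recorded.

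Third, every event count above is assumed, the intervals overlap heavily, and 8.4.4 plans no formal safety test. All of this stands, and it limits how strongly the point can be put. Sparse events are also the setting in which one or two lost patients can remove an arm's whole signal.

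Fourth, the Schedule lists CRP and ESR at months 6, 12 and 18 in all arms, so the standard-panel patient in Step 3 reflects missing data or a departure from the Schedule. That is fair, but an analysis set definition has to cope with such patients.

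**Conclusion.** The concern holds. As written, the plan removes from the between-arm safety comparison any patient with an event who never supplies both a questionnaire and a blood result after randomisation, and it gives two different FAS definitions. With 80 per arm and assumed SAE counts of 1 to 8, one lost SAE patient lowers that arm's SAE risk by 1.14 to 1.25 percentage points, and two lower it by 2.31 to 2.50. How many such patients there will be, and which arm the omission would favour, cannot be derived from the protocol. SAE recording and reporting to the sponsor and the primary estimate are not affected. It should be corrected because it puts an avoidable post-randomisation selection into a stated secondary objective.

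**What to change.** Make two text changes in section 8.4.1:

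1. State that safety is analysed in all randomised patients, the ITT Set already defined in 8.3, by allocated arm.
2. For efficacy, refer to the FAS as defined in 8.3 and delete the second definition.

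No extra data collection is needed. There are two small costs. Under the 8.3 definition, a patient with questionnaires but no ASDAS at any follow-up is not in the secondary efficacy analyses. In the all-randomised set, patients with little or no AE review slightly dilute the AE rates; reporting their number by arm would make that visible.

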8.4.2 Primary Endpoint

The primary endpoint is defined as the point prevalence of with low disease activity (defined as ASDAS <2.1) at the 6-, 12- and 18-months follow-ups.

The probability of being in low disease activity for repeated measures per individual will be used to estimate a risk difference across the three study arms. The primary variables will be analyzed using logistic regression mixed models with allocated study arm as primary explanatory variable. Other pre-specified covariates included in sensitivity analyses include age, gender, disease features. The SAP will detail these procedures, as well as alternative and further supportive evaluations, such as analyses including unbalanced baseline predictors or modifications of the regression model in case validity assumptions are not met. The primary analysis will be performed in the FAS. The primary endpoint will be evaluated by the p-value and confidence interval of the hypothesis test from the regression analysis.

In case the null hypothesis is not rejected, the new, follow-up strategies will be considered worse or inferior to usual care with hospital follow-up visits.

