4.1 Inclusion Criteria

Participants are eligible to be included in the study only if all the following criteria apply:

- Male or female >18 years of age at screening
- Patients with a diagnosis of axSpA who fulfil the diagnostic ASAS criteria for axSpA (see Appendix 9.4)
- Stable medical treatment with TNFi the last 6 months
- Inactive or low disease activity (ASDAS<2.1) at inclusion
- Capable of understanding the Norwegian language and of signing an informed consent form

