5.2 Measures to Minimize Bias: Randomization and Blinding

Eligible patients will be allocated in a 1:1:1 ratio between the three study arms. A statistician and a secretary, not involved in patient screening or enrollment, will provide a computer-generated block randomization list, and prepare sealed, opaque envelopes containing information on study arm assignment. Details of block size and allocation sequence generation will be provided in a separate document unavailable to those who enroll patients or assign treatment. The study does not include blinding of participant and treating health care personnel.

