7.2 Efficacy assessments

7.2.1 Patient-reported outcome measures

At Baseline (after screening, but before the randomization), patient demographics and PROs be collected using a digital device at the hospital.

Every 6. month, patients will receive a link a digital survey ("Nettskjema" (Services for sensitive data (TSD), University of Oslo)). Collection of a few PROs from patients will be done monthly for the Remote monitoring arm and every third month for the Patient-initiated care arm using the MyDignio app. The participants in these two intervention arm will also report blood test results every 6. month using the MyDignio app.

- **Patient global assessment of disease activity** (PGA) (Visual Analogue Scale, NRS 0-10) (All arms: Baseline, 6-, 12- and 18-months) (Remote monitoring arm: each month) (Patient-initiated care arm: each 3rd month)
- **Patient-reported flares** (All arms: 6-, 12- and 18-months) (Remote monitoring arm: each month) (Patient-initiated care arm: each 3rd month)
If the patient responds "yes" or "uncertain" to the question if they have experienced a significant worsening of symptoms (reflecting a flare in disease activity), they will be asked which date the flare occurred and the number of days it lasted.
- **Bath Ankylosing Spondylitis Disease Activity Index** (BASDAI) (All arms: Baseline, 6-, 12- and 18-months) (Remote monitoring arm: each month if disease worsening) (Patient-initiated care arm: each 3rd month if disease worsening)
BASDAI is a 6 item questionnaire (NRS 0-10) used to assess disease activity in ankylosing spondylitis³⁴. The score is the sum (of the first four individual questions and the mean of questions five and six) divided by five.
- **Bath Ankylosing Spondylitis Functional Index** (BASFI) (Baseline)
BASFI is a 10 item questionnaire (NRS 0-10) used to assess disease activity in ankylosing spondylitis³⁴. The score is the sum of each individual question divided by 10.
- **Patient-reported pain (general)** Single item (NRS 0-10) (Baseline, 6-, 12- and 18-months)

- **Patient-reported joint pain** Single item (NRS 0-10) (Baseline, 6-, 12- and 18-months)
- **Patient-reported global change in disease activity.** Single item with seven-point response scale ranging from "Much worse" to "Much better" (6-, 12- and 18-months)
- **Patient-reported global change in activity impairment.** Single item with seven-point response scale ranging from "Much worse" to "Much better" (6-, 12- and 18-months)

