7.2.4 Composite measures of disease activity

- **Ankylosing Spondylitis Disease Activity Score (ASDAS)** (Baseline, 6-, 12- and 18-months)

The ASDAS score is a 6-item composite measure of 4 PROs and CRP or ESR:

$\text{ASDAS}_{\text{CRP}}: 0.12 \times \text{back pain} + 0.06 \times \text{duration of morning stiffness} + 0.11 \times \text{patient global} + 0.07 \times \text{peripheral pain/swelling} + 0.58 \times \text{Ln}(\text{CRP}+1)$.

$\text{ASDAS}_{\text{ESR}}: 0.08 \times \text{back pain} + 0.07 \times \text{duration of morning stiffness} + 0.11 \times \text{patient global} + 0.09 \times \text{peripheral pain/swelling} + 0.29 \times \sqrt{(\text{ESR})}$.

ASDAS_{CRP} is preferred, but the ASDAS_{ESR} can be used in case CRP data are not available. CRP in mg/L; all patient assessments on a 10 cm scale. ASDAS <2.1 is regarded as an acceptable, low disease activity level²⁵. ASDAS is also a continuous measure, which makes it appropriate to assess potential changes in disease activity, and an increase of ASDAS>0.9 is considered a clinical important worsening²⁶.

- **Bath Ankylosing Spondylitis Disease Activity Index (BASDAI)** (Baseline, 6-, 12- and 18-months)

BASDAI is a 6 item questionnaire (NRS 0-10) used to assess disease activity in ankylosing spondylitis³⁴. The score is the sum (of the first four individual questions and the mean of questions five and six) divided by five.

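### The primary model omits baseline ASDAS, so the non-inferiority comparison gives up precision that would need no new data

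*Protocol*

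**What the plan says.** Section 8.4.2 states the primary analysis: "The primary variables will be analyzed using logistic regression mixed models with allocated study arm as primary explanatory variable". The next sentence places the covariates: "Other pre-specified covariates included in sensitivity analyses include age, gender, disease features". The SAP is to give the detail of these procedures and to add supportive evaluations, "such as analyses including unbalanced baseline predictors". The effect measure is a risk difference.

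Other sections show that baseline ASDAS will be available:

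- Section 4.1 makes it an entry condition: "Inactive or low disease activity (ASDAS<2.1) at inclusion".
- Section 7.2.1 times the patient-reported components: "At Baseline (after screening, but before the randomization), patient demographics and PROs be collected".
- Section 7.2.4 schedules ASDAS at baseline and at 6, 12 and 18 months, and notes that "ASDAS is also a continuous measure, which makes it appropriate to assess potential changes in disease activity".

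Section 5.2 says that a statistician and a secretary "will provide a computer-generated block randomization list" and names no stratification factor.

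**The concern.** Every patient enters with ASDAS below 2.1, so the binary endpoint is constant at baseline. The continuous score still varies: a patient entering just under the threshold would be expected to cross it more readily than one entering well below. This makes baseline ASDAS the natural prognostic covariate, and the design does not balance it by stratification.

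The covariate placement in 8.4.2 keeps it out of the primary model. If it counts as one of the disease features, it is assigned to sensitivity analyses; if it does not, it appears nowhere. The only stated response to chance imbalance is a supportive analysis with predictors found to be unbalanced, which is weaker than adjustment fixed in advance.

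Precision has direct consequences here. With 88% in low disease activity there are about 80 × 0.12 = 9.6 failures per arm at a visit. Section 8.4.2 also says that a strategy failing the test will be regarded as worse than usual care, so a wide interval would be read as inferiority.

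**Working it through.** **Inputs from the protocol.** 80 per arm, a 15-point margin, and a 5% level with multiplicity control whose sidedness and method are not given (8.2). An 88% rate of low disease activity (3.2), which is not stated to be the sample-size input.

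**Assumptions.** Correlation between baseline and follow-up ASDAS of 0.3 to 0.6 among enrolled patients, equal at each visit. Baseline drawn from a normal distribution with mean 1.3 and SD 0.6, cut to 0.3–2.1 (restricted SD 0.44). No true difference and no missing data. An 80% rate is shown as a second scenario.

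**The protocol's own power figure.** Section 8.2 claims about 80% power to show at least one new strategy non-inferior. With p = 0.88:

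- SE = √(2 × 0.88 × 0.12 / 80) = 0.0514, so the 95% half-width is 1.96 × 0.0514 = 0.101.
- Power for one comparison = Φ(0.15/SE − z). This is 83.1% at one-sided 0.025 and 75.1% at 0.0125.
- Power for at least one of two = 2Φ(c) − Φ₂(c, c; 0.5), where c = 0.15/SE − z and 0.5 is the correlation from the shared control arm. This is 93.2% and 88.0%.

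None of these is 80%. Values near it need inputs the protocol does not state, for example an 85% rate (81.3% for at least one at 0.0125). The stated figure cannot be checked from the protocol; it is not shown to be wrong.

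**One visit, adjusted against unadjusted.** There were 20,000 simulated two-arm trials per setting, comparing the raw risk difference with the standardised one from a logistic model with baseline ASDAS. Adjusted SE = unadjusted SE × √(variance ratio), and equivalent n = 80 / ratio.

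| Rate | Correlation | Variance ratio | Equivalent n per arm | Power at 0.025 | Power at 0.0125 |
|---|---|---|---|---|---|
| 88% | unadjusted | 1 | 80 | 83% | 75% |
| 88% | 0.3 | 0.971 | 82.4 | 84% | 76% |
| 88% | 0.6 | 0.865 | 92.5 | 88% | 82% |
| 80% | unadjusted | 1 | 80 | 66% | 55% |
| 80% | 0.3 | 0.961 | 83.2 | 68% | 57% |
| 80% | 0.6 | 0.822 | 97.3 | 74% | 65% |

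A separate simulation (baseline mean 1.4, SD 0.5, cut to 0.6–2.1; 3,000 trials per setting) gave ratios of 0.99, 0.91 and 0.78 at correlations 0.3, 0.5 and 0.7, for an 88% rate.

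**Three visits.** There were 1,500 trials per setting, with a random-intercept logistic model and the risk difference integrated over the random effect in both analyses.

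| Rate | Between-visit latent correlation | Target | Ratio at 0.3 | Ratio at 0.6 |
|---|---|---|---|---|
| 88% | 0.5 | visit average | 0.953 | 0.750 |
| 88% | 0.7 | visit average | 0.970 | 0.762 |
| 80% | 0.5 | visit average | 0.937 | 0.686 |
| 80% | 0.7 | visit average | 0.934 | 0.706 |
| 88% | 0.5 | 18 months, arm-by-visit | 0.965 | 0.827 |
| 80% | 0.5 | 18 months, arm-by-visit | 0.951 | 0.785 |

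**Chance imbalance.** One SD of the between-arm difference in mean baseline ASDAS is 0.44 × √(2/80) = 0.07. At 88% this moves the unadjusted difference by √(1 − ratio) × 5.14 points: √0.029 × 5.14 = 0.9 at correlation 0.3 and √0.135 × 5.14 = 1.9 at 0.6. The shift is already contained in the 5.1-point standard error and is not bias.

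**How the risk difference is derived.** Take true population rates of 88% and 73%, a 15-point deficit. Let the random-intercept variance be σ² = (π²/3) × ICC/(1 − ICC), solve for the linear predictors that give those rates after integration, then set the random effect to zero. The apparent deficit is 14.2 points at latent ICC 0.3 (92.2% v 77.9%), 12.9 at 0.5 (95.1% v 82.2%) and 9.8 at 0.7 (98.0% v 88.2%).

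**The case against.** The strongest reply is that nothing in 8.4.2 is invalid. An arm-only primary model with covariates in sensitivity analyses is a recognised choice, and calling arm the main explanatory variable need not list every term: the sentence does not mention visit either. Section 8.4 calls itself a summary and defers detail to a SAP that was not available here. The size of the gain rests on inputs the protocol does not give. At correlation 0.3 it is only 1% to 3% of the one-visit variance. A correlation of 0.6 after restriction implies roughly 0.7 without it, held constant to 18 months. On the protocol's own criterion (at least one strategy non-inferior), power at 88% is already 88.0% at one-sided 0.0125.

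Much of this stands. The comparison is valid, the gain may be close to nil if the correlation is weak or fades, and the largest reductions belong to the top of the assumed range. The 88.0% would rise to 88.7%–94.1% if baseline ASDAS explained 2% to 20% of the outcome variance. The deferral argument is weaker. The protocol does say where pre-specified covariates go, so a SAP that put baseline ASDAS into the primary model would depart from that text. It is also true that adding a covariate does not by itself shrink the standard error of a log odds ratio. The benefit comes through the standardised risk difference, which therefore has to be specified. The zero-random-effect distortion arises with or without the covariate; it bears on how the change is written.

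**Conclusion.** The concern holds, as a loss of efficiency. Validity and type I error are not affected. For one visit at an 88% rate and an assumed correlation of 0.3 to 0.6, the variance of the risk difference is 3% to 13% larger than it need be, measured as the reduction available. For the three-visit average the available reduction is 3%–5% at correlation 0.3 and 24%–25% at 0.6. At an 80% rate the corresponding figures are 4%–18% for one visit, and 6%–7% and 29%–31% for the three-visit average. All of these assume no missing data and a correlation that does not decline over 18 months; if it declines, the gain is smaller. The direction was the same in every setting examined. The change should be made because it is nearly free, although the trial does not depend on it.

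**What to change.** In section 8.4.2, and in the SAP to match:

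- Name continuous baseline ASDAS as a fixed covariate in the primary logistic mixed model.
- Obtain the risk difference by predicting each FAS patient's probability under each arm, integrating over the random-effect distribution (not setting the random effect to zero), and averaging over patients. The 15-point margin then still applies to a population-average difference.
- State the interval method: delta method or patient-level bootstrap.
- Keep the unadjusted model as a sensitivity analysis, and drop adjustment for predictors selected because they turn out unbalanced.

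The cost is a few sentences and slightly more programming, with no new data or visits. The integration step must be written out, because the shortcut understates a deficit and so favours non-inferiority. The change should be fixed before un-blinding, when section 8.4 says the SAP will be final.
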